Rationale: The resolution of all VS abnormalities has been proposed as an important primary endpoint for antibiotic trials in childhood pneumonia by the IDSA [62]. In contrast to adults, severe morbidity and mortality from CAP is minimal in children, particularly for *Mp* CAP (section 3.5 and 3.7). Previous trials on macrolides for *Mp* CAP have mainly focused on fever duration as a key endpoint [31, 32]. In the myCAP study, the median body temperature (T) at presentation among myCAP patients was 39.1°C (IQR, 39.0-39.7), and the clinical diagnosis of CAP based on fever and tachypnea could be radiologically confirmed in 98% of the cases [43]. On room air, 17% *Mp* CAP patients had an SpO₂<93% and required additional oxygen supply. The median fever duration for *Mp* CAP children was 2 days. There were no statistically significant differences between patients with or without antibiotic treatment for *Mp* [43]. Lu et al. [63] observed a mean fever duration of 5 days (no statistically significant differences between patients treated with macrolides or placebo). To conclude, this study will use VS measurements taken at the timepoint before randomization as baseline measurements. The VS measurements will be followed up until normalization of VS to reference values. We expect a rate of <1% of patients' VS not normalizing within a 28-day FUP. In agreement with the IDSA considerations [62], an assessment of the time to VS normalization (T, RR, HR, SpO₂) has been selected to be of main interest for MYTHIC.

1.2: CAP-related change in patient care status within 28 days (safety)

Defined as any change in patient care status from an ambulatory to hospitalized setting (admission or re-admission), or from a hospitalized on general ward to an ICU setting (ICU transfer).

Specific measurement: Incidence of (re-)admission to hospital or transfer to the ICU.

Analysis metric: Final value.

Method of aggregation: Proportion.

Time point: Within 28 days after randomization.

Rationale: We expect the placebo to be non-inferior to macrolides treatment regarding a CAP-related change in patient care status. This non-inferiority will be assessed by the incidence of (re-)admission to

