6.3 Unblinding procedures (code break)

In the MYTHIC, no situations needing emergency unblinding are foreseen. AEs caused by drug toxicity and needing discontinuation of the drug are expected to be extremely rare when administering azithromycin in regular doses and for 5 days. The acute toxicity of a one-off azithromycin overdose is very limited. There is no specific antidote and management is symptomatic. Allergic reactions to any of the ingredients of the formulation can occur. However, these are extremely rare. In situations where an allergic reaction due to trial treatment is suspected, and further regimen doses are due, trial treatment is to be discontinued. The following criteria for discontinuation or modification (Table 6) guarantee safety in MYTHIC without the necessity of unblinding the IMP:

Table 6. Criteria and procedures for discontinuation or modification of the IMP.

Discontinuation criteria:	Modification criteria:

 Any change in the patient's condition that justifies the discontinuation of the IMP (e.g., need for ICU transfer). Unacceptable toxicity or AE (according to the prescribing information). Use of a medication with a known major drug interaction with azithromycin. Withdrawal of informed consent for IMP by patient/parent. 	
Ambulatory patients:
 
 Need for hospital admission. 
Hospitalized patients:
 
 Failure to maintain oxygen saturation $\geq 90\%$ with FIO_2 100%. Oxygen saturation $< 90\%$ for $> 48h$. Clinical features of severe respiratory distress/exhaustion and/or shock/sepsis.
Procedures:	Procedures:

 Stop IMP 	
 Treatment modification with antibiotics against atypical pathogens* and/or Switch to standard of care**

Important note: Decision about additional treatment with beta-lactams (such as amoxicillin) to avoid potential non-treatment of co-infecting bacterial pathogens (e.g., Streptococcus pneumoniae) in study patients will be made by the treating physician and will not be influenced by local investigators or TMT.*/**
	

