* Treatment alternatives to the IMP (azithromycin as active drug) against atypical pathogens (e.g., *Mycoplasma pneumoniae*, *Chlamydia pneumoniae*) must be discussed between the local investigators and the TMT. These include clarithromycin (as another potent macrolide) or doxycycline in children ≥ 8 years of age (also as treatment option for infections with MRMP) [9]. In case of clinical suspicion of MRMP infection (e.g., worsening and/or non-responding symptoms), testing and (modifying) treatment for MRMP should be initiated irrespective of the study. The TMT will also support the local team at the participating centers in managing infections with (possible) MRMP.

** Decision about switch to standard of care (defined as treatment-as-usual, usual care, or routine care) will be made by the local team. The IMP should be continued for the total 5-day treatment duration whenever possible.

In case of need for emergency unblinding due to unforeseen circumstances in a study participant, the coordinating principal investigator or TMT must be contacted. They will be available around the clock by phone in case an emergency unblinding is deemed necessary. Unblinding of the respective study participant will occur through the secuTrial® database by a person with an appropriate right.

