11.4.1 Datasets to be analyzed, analysis populations

The full analysis set (FAS) will include **all patients who gave written informed consent and were enrolled**. Patients in the FAS will be analyzed according to the randomly assigned treatment, adhering to the intention-to-treat principle.

The per protocol set (PPS) will include all patients from the FAS who are **Mp PCR-positive** (section 6.1, Table 5) and who are sufficiently compliant to treatment ($\geq 80\%$ of the medication used).

The strict per protocol set (strict PPS) will include all patients from the PPS who additionally have **confirmed Mp infection by IgM ASC ELISpot assay** (section 6.1, Table 5).

Patients in the PPS and strict PPS will be analyzed according to the received treatment (in case there are any deviations from the randomized treatment).

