11.4.2 Primary analysis

To assess the non-inferiority of placebo vs. azithromycin regarding the co-primary endpoint **time to**

normalization of VS, we will estimate the hazard ratio of placebo vs. azithromycin with a two-sided 97.5% CI using a Cox proportional hazards model on the PPS (defined in section 11.4.1). Non-inferiority of placebo will be declared if the lower limit of the CI will be larger than the non-inferiority margin (i.e., the whole CI lies entirely above the margin).

To assess the non-inferiority of placebo vs. macrolide regarding the co-primary endpoint **CAP-related change in patient care status**, we will estimate the absolute risk difference ($ARD = risk_{azithromycin} - risk_{placebo}$) with a two-sided 97.5% CI on the PPS. Non-inferiority of placebo will be declared if the lower limit of the CI will be larger than the non-inferiority margin (i.e., the whole CI lies entirely above the margin).

The two non-inferiority tests will be performed and interpreted independently (of each other) and the trial considered successful if non-inferiority can be shown for at least one of the primary outcomes. Should the resulting CIs exclude the reference value for no difference (1 for hazard ratio, 0 for ARD), the result can be interpreted as superiority of either treatment [88].

To complement the main analyses above, the following sensitivity and additional analyses are planned:

- We consider the **PPS as the main set for showing non-inferiority** (section 6.1, Table 5), and the sample size calculation was also done with regard to the PPS (section 11.2). In addition, we will also test non-inferiority in the strict PPS and the FAS. Since the three analysis sets (FAS, PPS, and strict PPS) differ considerably in size and composition (section 6.1, Table 5), we will consider the PPS as the relevant set for concluding non-inferiority, but we will discuss differences in the conclusions based on the different sets. For a robust interpretation of the non-inferiority test these analyses should lead to similar conclusions as the main analysis [87].
- For CAP-related change in patient care status, we will present the 2×2 table of events per treatment arm and an unadjusted odds ratio (OR) estimate for all three analysis sets.
- For time to VS normalization, we will plot Kaplan-Meier curves and estimate median time-to-event by trial arm.

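### The 80% medication rule has no exception for an IMP stop under Table 6, so a child with an early care-status event can drop out of the per protocol set that decides non-inferiority

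*Protocol*

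**What the plan says.** **The event.** Protocol 5.1 defines co-primary outcome 1.2 as a CAP-related move from ambulatory care to hospital, or "from a hospitalized on general ward to an ICU setting (ICU transfer", within 28 days.

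**What happens to the IMP.** Table 6 (section 6.3) has two columns.
- The discontinuation column covers any change in condition "that justifies the discontinuation of the IMP (e.g., need for ICU transfer", and its only procedure is to stop the IMP.
- The modification column includes, for ambulatory children, "Need for hospital admission". Its procedures are "Treatment modification with antibiotics against atypical pathogens* and/or" a switch to standard of care. Stopping the IMP is not listed there.

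The single-asterisk footnote calls the open-label drugs "Treatment alternatives to the IMP (azithromycin as active drug) against atypical pathogens". The double-asterisk footnote, attached to the switch to standard of care, adds "The IMP should be continued for the total 5-day treatment duration whenever possible". Section 8.6 allows the IMP to be modified with another antibiotic, without saying whether the IMP stops, and expects this to be rare and without effect on the results.

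**Who is analysed.** Section 11.4.1 admits to the PPS children who are PCR-positive "and who are sufficiently compliant to treatment", set at 80% or more of the medication used. On the choice of set, 11.4.2 says "we will consider the PPS as the relevant set for concluding non-inferiority". The trial succeeds if either co-primary outcome is met.

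**The concern.** Two of the Table 6 triggers, ICU transfer and admission of an ambulatory child, are themselves the co-primary safety event when they are CAP-related. A stop or replacement made because of that event lowers the share of medication used, and the 80% rule then reads the shortfall as non-compliance. The child is removed from the primary safety analysis because of the outcome.

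Such exclusions fall more heavily on the arm that deteriorates more. If that is placebo, the observed risk difference moves towards 0, which is the error a non-inferiority test has to guard against. Because one co-primary success is enough, a result on 1.2 in the PPS alone could carry the trial.

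The multiple imputation in 11.5 does not help, since these children are excluded by definition and their outcomes are not missing. The 14.5% inflation in 11.2 covers the loss of numbers, not the bias.

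**Working it through.** **1. The plan's own figure.** Inputs from 11.2: risk 5% in both arms, margin 7.5 points, one-sided alpha 1.25%, power 80%, drop-out 14.5%.

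n per arm = (2.241 + 0.842)² × 2 × 0.05 × 0.95 / 0.075² = 160.5, so 161 per arm and 322 in total. 322 / 0.855 = 376.6, against the stated 376. The figure reproduces.

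**2. When does a stop fall below 80%?** Volumes from Table 7:

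| Basis | after dose 1 | 2 | 3 | 4 | 5 |
|---|---|---|---|---|---|
| 15 to <20 kg (3.75 mL, then 2.00 mL; total 11.75 mL) | 31.9% | 48.9% | 66.0% | 83.0% | 100% |
| all other weight bands | 33.3% | 50.0% | 66.7% | 83.3% | 100% |
| number of doses | 20% | 40% | 60% | 80% | 100% |

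By volume or by dose count, a stop before dose 4 excludes the child and a stop after dose 4 does not.

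**3. Weight of one event.** 322 × 0.05 = 16.1 expected events, so each lost event is 1/16.1, about 6% of them.

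**4. Effect on the difference.** Let f be the share of 1.2 events that occur before dose 4 and end the IMP, assumed equal in both arms. After exclusion a true risk p becomes p(1−f)/(1−pf). At the margin (azithromycin 5%, placebo 12.5%):

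- f = 5%: 0.11875/0.99375 = 11.95% vs 0.0475/0.9975 = 4.76%; difference 7.2 points
- f = 10%: 0.1125/0.9875 = 11.39% vs 0.045/0.995 = 4.52%; difference 6.9 points
- f = 25%: 0.09375/0.96875 = 9.68% vs 0.0375/0.9875 = 3.80%; difference 5.9 points

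With equal true risks both arms change alike and the expected difference stays 0.

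**5. Effect on the test.** Simulation with 400,000 runs and 161 per arm before exclusion. Non-inferiority is declared if the lower limit of the two-sided 97.5% CI exceeds −7.5 points. The protocol does not name the interval, so two are shown.

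| f (assumed) | False non-inferiority, Newcombe | Wald |
|---|---|---|
| 0 | 1.2% | 1.6% |
| 5% | 1.5% | not run |
| 10% | 1.9% | 2.8% |
| 25% | about 4% | 6.4% |

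The f = 0 row is what the proposed rule gives if every such event is retained.

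**The case against.** **Stopping is not automatic.** A reader might infer that every early ICU transfer is excluded. The text does not go that far: ICU transfer is an example of a change that justifies a stop, 7.4 says a patient may be stopped, and 8.3 says discontinuation may occur. Severe respiratory distress and shock are in the modification column. A stop at ICU transfer is expected, not certain. This limits the size of the problem but does not remove it.

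**The IMP status at modification is mostly clear.** The single-asterisk footnote reads as replacement after discussion with the trial management team, and the instruction to continue belongs to the standard-of-care route. A reader might infer that children are left without treatment, or that double macrolide exposure is a real hazard. The documents do not support either: antibiotics are provided for in Table 6 and 8.7, and a known major drug interaction is already a reason to stop the IMP. What stands is a wording gap that lets PPS membership depend on how a site reads the table.

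**Large error rates.** With f at 50% the simulated rate reaches 15% (Newcombe) or 25% (Wald). Nothing in the protocol supports so high a share. An affected event must be CAP-related, fall in the first days of a 28-day window and end the IMP, and section 3.5 describes fulminant disease as very uncommon. At f of 5-10% the shift is comparable to the choice between Newcombe and Wald.

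**Safeguards and the SAP.** The full analysis set (FAS) is also tested, 2×2 tables are given for all three sets, and similar conclusions are expected for a robust interpretation. These make a discrepancy visible, but 11.4.2 keeps the PPS decisive and only promises discussion. A separate SAP may define how use is counted. However, the 80% rule and the deciding set are fixed in the protocol without an exception, so this is a stated rule rather than a detail left open.

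**Conclusion.** The point holds. As written, 11.4.1 can remove a child from the primary analysis of the safety endpoint because that child had the endpoint early. It follows from the 80% rule, the dose shares in Table 7, the stop for ICU transfer in Table 6 and the primacy of the PPS. For admissions of ambulatory children it applies only where the site replaces the IMP.

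The bias exists only if placebo is truly worse, and then favours non-inferiority. Its size depends on f, which the protocol does not give. The illustrative false non-inferiority rates of 1.5% to about 4% (Newcombe, f = 5-25%) assume a truth exactly at the margin and equal f in both arms; they are not a forecast. With about 16 expected events, even one or two exclusions count, so the assurance in 8.6 does not hold for the PPS. The point should be fixed. It does not undermine the sample size, which reproduces.

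**What to change.** **In 11.4.1.** State that an IMP stop or replacement under Table 6 for CAP deterioration is not non-compliance, and that the 80% is counted against doses due up to that stop. The child and the event then stay in the PPS for co-primary 1.2. Stops for toxicity, drug interaction or withdrawal remain under the present rule.

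**For co-primary 1.1.** Report the result under both this rule and the present 80% rule, because normalization under rescue treatment would count for the assigned arm and may favour placebo.

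**Secondary wording note, Table 6 and 8.6.** Say that the IMP stops when an open-label macrolide or doxycycline is started for CAP deterioration, and that the instruction to continue applies only to a switch to standard of care without such a drug.

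**Cost.** One sentence in 11.4.1, two in 6.3/8.6, a note to sites, and the date and reason of IMP stop in the eCRF (8.6 already records modifications). No extra patients and no unblinding. The downside is that the PPS will hold a few children who received few doses, possibly only one.

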7. STUDY POPULATION AND INFORMED CONSENT PROCEDURE

7.1 Eligibility criteria

Inclusion criteria:

Inclusion criteria for screening phase:

- **Children aged 3-17 years** (from 3rd up to 18th birthday) presenting to the ED who will be managed ambulatory or will be admitted to general ward.
- **Clinical diagnosis of CAP:**
 - 1) **Diagnosis defined as the treating physician's documented diagnosis of CAP;** AND
 - 2) **Fever $\geq 38.0^{\circ}\text{C}$** (measured by any method [i.e., ear, axillary, rectal, or forehead site] in the ED or via parent report observed in the last 24h); AND
 - 3) **Tachypnea** (RR above the age-specific reference value as defined in section 5.1, Table 1 during the assessment in ED [triage or clinical examination]).

This trial aims to produce translational results generalizable to a “real-world” setting. In ED settings, the diagnosis of CAP is generally based on clinical criteria [8, 9]. Therefore, inclusion criteria for this study will not be based on radiological or laboratory diagnostics. However, according to our experience from previous studies and feedback from participating centers, we expect $\geq 90\%$ of children to have a CXR performed as part of their diagnostic routine.

- **Written screening consent for participation in screening phase** signed by parents or legal guardians and the patient if ≥ 14 years of age.

Additional inclusion criteria for intervention phase:

- **Positive *Mp* screening test result** with the *Mp* IgM LFA (grade 2 or 3) (section 6.1).
- **Written informed consent for participation in intervention phase** signed by parents or legal guardians and the patient if ≥ 14 years of age.

Exclusion criteria:

Exclusion criteria for screening phase:

- None.

Exclusion criteria for intervention phase:

- Contraindication to azithromycin: Documented allergy to azithromycin; cardiovascular disease, including bradycardia, arrhythmias, and/or QT-interval prolongation*; myasthenia gravis.
*Co-medication with arrhythmogenic or QT-interval-prolonging drug (<https://crediblemeds.org>) is no exclusion criteria but will be discussed with the local investigators and/or TMT.
- Underlying comorbidities: Cystic fibrosis or other chronic lung disorders (excluding asthma), primary or secondary immunodeficiency, sickle-cell anemia, or severe cerebral palsy.
- History of recurrent pneumonia (two or more episodes) or severe pneumonia (ICU admission or complications of CAP such as lung abscess, effusion, and empyema) in lifetime.
- Antibiotic treatment against *Mp* within the previous 7 days, including macrolides, tetracyclines, or fluoroquinolones.
- Referral to ICU directly from the ED (e.g., development of respiratory failure).
- Inability to tolerate oral medication.
- Parents are unlikely to reliably complete FUP visits and questionnaires (e.g., due to language barriers or living far from the study site).

7.2 Recruitment, screening, and informed consent procedure

Patient information material about the MYTHIC Study will be provided to participating centers in form of a short one-page DIN A5 flyer with a QR code to the MYTHIC website that can be placed in the waiting areas of the ED. The MYTHIC website (www.mythic-study.ch) will be created with both public and member-only areas, including a short informational film. Any information material reviewed and endorsed by the relevant CEC will be also deposited in the publicly accessible area of the MYTHIC website.

The ED staff (triage nurse or treating physician) will inform the local investigators (study nurse, study physician, or GCP-trained ED consultant) about an eligible patient with diagnosis of CAP (pre-screening). The local investigators will check inclusion criteria for the **screening phase** and initiate contact. Eligible patients and/or their parent will receive a consent form for research projects with persons (HRO, chapter 2) providing sufficient information about the screening phase of the study to make an informed decision. The local investigators will obtain written screening consent, and perform the screening with the *Mp* IgM LFA from capillary blood and collect a NPS for *Mp* PCR. The *Mp* IgM LFA results will be available within 10min and will be communicated to the treating physician. In case of a positive *Mp* IgM LFA result, written informed consent for **intervention phase** participation will be obtained at the ED (for ambulatory patients) or as closely as possible to hospital admission (for hospitalized patients) within maximum 6h after the ED admission. This corresponds to randomization within 10h from presentation to the ED and will therefore provide time for parent (and patient) to read the consent.

All patients will be assessed against the inclusion and exclusion criteria as listed in section 7.1 for both the written screening consent (screening phase) and written informed consent (intervention phase), and will be considered eligible for enrollment into MYTHIC if they fulfill *all* the inclusion criteria and none of the exclusion criteria. There will be no exceptions to eligibility requirements at the time of randomization. Questions about eligibility criteria should be addressed prior to randomizing a participant. Eligibility will be reviewed and documented by a local investigator at each participating center before patients are randomized into the study.

Written informed consent to enter into MYTHIC and be randomized must be obtained from the parent (and patient) after explanation of the aims, methods, benefits, and potential hazards of the respective phase of the trial and before any trial-specific procedures are conducted. Written informed consent (intervention phase) may only be obtained once eligibility has been confirmed.

It must be made completely and unambiguously clear that the parent (and patient) is free to refuse to participate in all or any aspect of the trial, at any time and for any reason, without incurring any penalty or affecting the treatment of the patient.

The informed consent process must be documented in the clinical information system, the signed consent forms must be kept by the local principal investigators and documented in the eCRF, and a copy given to the family. The pediatrician/general practitioner of the patient will be informed about participation in MYTHIC with the ED and/or hospital letter (including a separate paragraph with information about the trial, medication ID, and FUP procedures).

Further information on recruitment and screening are described in section 6.1 and shown in the Study flow (page 29).

Families will not be compensated for participating in the MYTHIC Study.

